7.2.11. Photography – 3D

3D Image capture will be used to evaluate baseline and post-procedure changes regarding the depth and volume of nasal collapse at approximately two sites. 3-D photography review will be limited to approximately 3 sites, and subject participation is optional. Site selection for participation will be based on adequate facility space and staff to support this additional component. Subject participation in 3D photography is optional.

3D Images will be taken to record baseline NVC of both the left and right side of the nose under static conditions and at inhale. Static and inhales images for both sides will be taken at 3, 6 and 12 month time points, to evaluate the change in the nasal collapse depth from baseline.

The Canfield Vectra H1 handheld imaging system allows for the capture and analysis of 3D images. The system is comprised of the Vectra H1 camera, Mirror[®] software and VECTRA Analysis Module. The Vectra H1 camera has an integrated flash to simultaneous capture photographs from dual-angles to build 3-D images. Photographs are either captured to the camera's SD card or tethered to a workstation. Photographs are captured and managed using Canfield Mirror[®] software and is analyzed with Canfield VECTRA Analysis Module. Images will be saved with the camera-generated sequence number (e.g. photo "38"), and then transferred for analysis using the subject ID and study visit for identification. See Addendum D "3D Imaging Procedure" for comprehensive image capture and analysis procedures.

Images will be transferred using BrickFTP site.

See Addendum E "3D Camera Imaging Procedure".

7.2.12. Assessment of Turbinate Hypertrophy Contribution to NAO

After completion of all other assessments at the Baseline Visit, subjects will be asked to assess their ability to breath after a decongestant (e.g. Afrin) has been administered. Administration of a decongestant is frequently used to diagnose significance of inferior turbinate contribution to NAO. After decongestant administration, subjects will be asked to rate their degree of nasal airway obstruction using the VAS scale (See Section 7.2.2).

Spirox Latera™ implant support of lateral wall cartilage (LATERAL-OR) study	
SPI-CP-301	Sept

7.2.13. Subject Satisfaction Questionnaire

The subject satisfaction questionnaire is a PRO form that will contain the questions related to subject satisfaction with the procedure and their nose appearance. Subjects will complete the Questionnaire at the 1 Month, 3 Month, 6 Month and 12 Month visits.

7.2.14. Discretionary Imaging

In addition to the protocol specific imaging outlined above, the Investigator may wish to share, or Spirox may request, additional images (digital photos) or videos of subject for the purposes of, but not limited to, consultation (e.g. placement of device ahead of procedure, etc.), documentation of changes (e.g. cosmetic change, lateral wall motion, etc.) or adverse event reporting (e.g. image of hematoma). Images may include endoscopic nasal video, digital video or photography. Images or videos may be taken at any time point during the study.

Digital images will be blinded (e.g. black boxes placed over the eyes). Images may be used for educational and/or research purposes. Images or videos will be transferred to Spirox using BrickFTP.

7.2.15. Latera[™] Patient Experience and Testimonials

Subjects that have enrolled in the study may also be invited to participate in "Latera™ Patient Experience and Testimonials". This invitation may occur at time of Screening or at any time point through study exit.

Spirox may choose to capture Latera[™] patient experience and/or testimonials through film, videotape, photographs and/or quotes. Spirox may choose to capture the testimonials prior to, during and after the LATERA procedure is performed, at varying intervals (i.e., day of procedure, 1 week post-procedure, 1 month post-procedure, etc.). Spirox and the investigational sites may use these photographs, videos, personal images and quotes in whatever medium deemed appropriate by Spirox for any of the following purposes: (i) educational and research purposes, (ii) medical or audiological consultations, (iii) publication in professional journals, (iv) collateral and promotional materials, (v) web-based marketing materials including website content, (vi) public and media relations, or any other advertising methodology.

For these subjects, written consent in the form of an IRB approved addendum to the study ICF will be required. Participation is optional and will not impact their participation in the study. Consent to participate does not guarantee that they will be selected as a participant. No additional reimbursement beyond what is outlined in Section 5.3 will be provided.

7.3. LOST TO FOLLOW-UP

Site personnel should make reasonable efforts to ensure that all subjects complete the requisite follow up visits. A subject will be considered lost to follow-up if the site has:

- 1. Attempted to contact the subject with a minimum of two phone calls; and
- 2. Has mailed a certified letter to the subject.

Before a subject is considered lost to follow up, the above described attempts to contact the subject must be documented in the subject's medical records and in the study CRFs.

Version 2.0 ember 7, 2017

7.4. STANDARD OF CARE STUDY PROCEDURE

Per an investigator's decision, subjects may receive concomitant septoplasty and/or turbinate reductions in addition to placement of the Implants to address other potential causes for the nasal airway obstruction.

Septoplasty is a common surgical procedure to correct a deviated septum — a displacement of the bone and cartilage that divides the nasal passages. During the procedure, the lining (the mucosa) is first lifted off the cartilage and bone. The cartilage and bone can then be reshaped. Sometimes, portions of the cartilage and bone need to be removed. The lining is then laid back down.

Turbinate reduction or turbinate resection is a common procedure that is performed alone or in conjunction with septoplasty. There are two commonly used approaches to reduce turbinate size: radiofrequency reduction, and microdebrider-aided resection using a submucosal approach. With this procedure, the lining of the turbinate is left intact, but the tissue from the inside of the turbinate is removed. As the turbinate heals, it becomes smaller than before surgery.

Septoplasty and/or turbinate reductions procedures are well established and considered standard of care to address respective etiologies. Treatment of the lateral wall with Latera alone or in conjunction with these procedures is being evaluated in this study.

7.5. CONCOMITANT MEDICATIONS, TREATMENTS, AND PROCEDURES

Implant procedure may be completed in conjunction with Septoplasty and/or Turbinate reduction procedure(s).

Current medications related to the treatment of NAO, NVC, and the management of nasal allergies will be documented in the eCRFs.

7.6. PROHIBITED MEDICATIONS, TREATMENTS, AND PROCEDURES

Concomitant medications or therapies preventing subjects from being eligible to participate in this study are current use of nasal oxygen, CPAP, chronic use of systemic steroids and/or recreational intra-nasal drugs. Additionally, concomitant radiation exposure in the treatment area or chemotherapy will deem a subject ineligible to participate.

In addition, according to the study protocol, the following treatments are not permitted concurrent with index procedure or within 24 months after index procedure:

- Functional Endoscopic Sinus Surgery (FESS)
- Sinuplasty procedure
- Rhinoplasty procedure
- Any surgical or non-surgical treatment of the nasal valve, other than the index procedure, within 12 months of the study
- Use of a dilator and/or an external device in the nasal area (e.g. nasal strips).

Spirox Latera™ implant support of lateral wall cartilage (LATERAL-OR) study	Version 2.0
SPI-CP-301	September 7, 2017

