7.1.4. Follow-Up Evaluation Visits (Visit 4-9)

Safety and performance data will be collected at 1 month (+/- 7 days), 3 months (+/-15 days), 6 months (+/- 15 days) 12 months (+/- 30 days), 18 months (+/- 30 days) and 24 months (+/- 30 days) post procedure.

A detailed description of the visit assessments and evaluations are located in Section 7.2. The following data will be collected:

- 1. NOSE scale (See Section 7.2.1)
- 2. NAO Breathing Assessment (See Section 7.2.2)
- 3. Subject Satisfaction Questionnaire (See Section 7.2.13)*
- 4. Post Procedure Health Economics Questionnaire (See Section 7.2.4)*
- 5. Update Concomitant Medications, if changed (See Section 8.9)
- 6. Adverse Events since last visit (See Section 8)
- 7. Post Procedure Nasal Exam (see section 7.2.7)*
- 8. Lateral Wall Motion Video 6 Month Visit only (See Section 7.2.9)*
- 9. Photography Cosmetic (select sites only) 3 and 6 Month Visits only (See Section 7.2.10)*
- 10. Photography 3D (select sites only) 3, 6 and 12Month Visits only (See Section 7.2.11)*

*This assessment/evaluation will not be collected at the 18 month and 24 month follow ups

Spirox Latera™ implant support of lateral wall cartilage (LATERAL-OR) study	Version 2.0
SPI-CP-301	September 7, 2017

Adverse events observed through the 12 month visit will be collected and documented. Only adverse device effects will be collected beyond the 12 month visit. Spirox will be notified as necessary pursuant to the description provided in Section 8. Data collected for these visits should be entered into the EDC no later than seven (7) days after the completion of each visit.

Upon completion of the follow-up visit activities, the subject will be scheduled for the next Follow-up Evaluation Visit.

Subject participation will be complete at the 24 month follow-up time point and documented in the Study Exit eCRF.

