7.2.4. Post Procedure Health Economics Questionnaire

The post procedure health economics questionnaire administered post-procedure is different from the version completed at baseline in the timeframes being referenced. The post-procedure health economics survey will assess frequency and type of doctor visits related to the Nasal Airway Obstruction condition since the index procedure. Do not include visits related to the study when recording the frequency. Subjects will complete the Questionnaire at the 1 Month, 3 Month, 6 Month and 12 Month visits.

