7.7. STUDY SCHEDULE OF EVENTS TABLE

Study Events	Screening & Enrollment (Visit 1)	Baseline Evaluation (Visit 2) ¹	Treatment (Visit 3)	Follow Up 1 mo (Visit 4)	Follow Up 3 mo (Visit 5)	Follow Up 6 mo (Visit 6)	Follow Up 12 moStudy Visit (Visit 7)	Follow Up 18 & 24 mo/Final Study Visit (Visits 8 & 9)	Early Exit
Secure Informed Consent	Х								
Secure Re-Consent for 18M and 24M Follow Up							Х		
Inclusion/Exclusion	Х		X ²						
NOSE Scale (PRO) ³	Х	Х	X ²	Х	Х	Х	Х	Х	
NAO Breathing Assessment (PRO)		Х		Х	Х	Х	Х	Х	
Subject Satisfaction Questionnaire (PRO)				Х	Х	Х	Х		
Health Economics Questionnaire (PRO)		Х		Х	Х	Х	Х		
Nasal Medical History/Nasal Geometry		Х							
Nasal Exam		Х		Х	Х	Х	Х		
Lateral Wall Motion Video		Х				Х			
Photography- 3D Camera (select sites)		Х			Х	Х	Х		
Photography –Cosmetic (select sites)		Х			Х	Х			
Turbinate Hypertrophy Contribution to		Х							
NAO assessment (Nasal Decongestant)									
Photography – Planning Images			Х						
NAO Treatment			Х						
Concomitant Medications		Х	Х	Х	Х	Х	Х		
Adverse Event Assessment			X	X	X	X	Х		Х
Adverse Device Effects Assessment								X	
Complete Study Exit Form								X ⁴	Х

¹ Visit 2 activities may be done in conjunction with Study Visit 1. In this instance, the Screening NOSE Scale is not required.

² If Visit 3 (Treatment Visit) is more than 1 month after Visit 1, inclusion/exclusion criteria need to be re-confirmed. Additionally, subjects should be asked to review IC form, initial and date the IC document to confirm continued consent for participation, and complete NOSE scale.

³ If Visits 1, 2 and 3 are done on the same day, the Screening and Treatment NOSE Scales are not required.

⁴To be completed at 24M follow up.

Spirox Latera™ implant support of lateral wall cartilage (LATERAL-OR) study	
SPI-CP-301	Sep

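### Nasal procedures after month 12 are not asked about at the 18- and 24-month contacts, and Protocol 7.6 gives both 24 and 12 months for nasal-valve treatment, so a retreated subject can count unnoticed as a late responder

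*Protocol*

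**What the plan says.** **Prohibition period.** The lead-in to the second list in Protocol 7.6 states that "the following treatments are not permitted concurrent with index procedure or within 24 months after index procedure". Sinus surgery, sinuplasty and rhinoplasty have their own bullets with no other period. So does "Use of a dilator and/or an external device in the nasal area". The bullet on any other treatment of the nasal valve carries its own limit: "other than the index procedure, within 12 months of the study". Exclusion criteria 4 and 7 (Protocol 5.2) also use twelve months.

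**Late contacts.** The 18- and 24-month evaluations may be an office visit, a telephone interview or a mailed form (Protocol 5.3). For the starred items in Protocol 7.1.4, which include the Health Economics Questionnaire and the nasal exam, the footnote reads "This assessment/evaluation will not be collected at the 18 month and 24 month follow ups". On safety, 7.1.4 adds "Only adverse device effects will be collected beyond the 12 month visit", while Protocol 8.1 keeps serious adverse events and device effects to the end of participation. The item "Update Concomitant Medications, if changed" has no star, yet the "Concomitant Medications" row in the 7.7 table is blank for Visits 8 and 9.

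**Endpoint and analysis.** Responder rates and VAS change at 18 and 24 months are secondary endpoints (Protocol 4.2.2). The rates use the same technique as the primary (10.4.3). Response depends on the NOSE score only (10.4.2; SAP 4.2.1). The SAP repeats the efficacy analyses in the per-protocol set (section 4). That set leaves out subjects with major deviations or events that might affect NOSE scores (2.2.1, 3.6).

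**The concern.** The late endpoints describe how the result holds up after the implant has been absorbed, which takes about 18 months (Protocol 6.2). This is when further treatment of a returning obstruction would blur the picture most. Suppose a subject has a valve procedure at month 15 and scores well at month 24. On NOSE alone that subject is a responder, and no item listed for the late contacts would bring the procedure to light. If the 12-month bullet governs, valve treatment in months 12 to 24 is not a deviation at all, so nothing obliges a site that does hear of it to log it as one. Reported late response could then partly reflect later treatment, with no means of telling how far.

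**Working it through.** **Step 1: which period applies.** Rhinoplasty, sinus procedures and dilators take the 24-month lead-in without dispute. Only other nasal-valve treatment between months 12 and 24 is ambiguous. The revision history says the current version added the 18- and 24-month evaluations, so the 12-month wording may be left over. That is an inference and the documents do not say so.

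**Step 2: what could reveal a treatment after month 12.**

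| Source | At 18 and 24 months? | Would it reveal a procedure or dilator? |
|---|---|---|
| NOSE and VAS (7.1.4, 7.7) | Yes | No; neither asks |
| Adverse device effects (7.1.4, 8.1) | Yes | Only if the event is a device effect |
| Serious adverse events (8.1) | Yes | An elective outpatient valve procedure need not be one |
| Health Economics Questionnaire, which is to "assess frequency and type of doctor visits related to the Nasal Airway Obstruction condition since the index procedure" (7.2.4) | No; last at 12 months | Could prompt it, but has ended |
| Nasal exam (7.1.4, 7.7) | No | Could prompt it, but has ended |
| Concomitant medications | 7.1.4 yes, 7.7 blank | Covers drugs (7.5). May reach dilators, because 7.2.5 groups nasal airway devices with medications. Not surgery |
| Exit form (7.7) | 24 months only | Contents not shown |

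**Step 3: size.** The documents give no rate of later treatment, so these are assumptions: N = 150 at 24 months (the 5.3 target) and k = 3, 8 or 15 treated after month 12.

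- Largest gap between the observed rate and one counting treated subjects as non-responders = k/N. It is reached when all k are observed responders.
- Inflation in the sense of response caused by the later treatment = k × c / N, where c is the share of treated subjects turned from non-response to response. If they would otherwise respond at the 66% planning rate, c is at most 1 − 0.66 = 0.34.

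| k | Share of 150 | Largest gap, k/150 | Inflation, c = 0.34 | Inflation, c = 1 |
|---|---|---|---|---|
| 3 | 2.0% | 2.0 points | 0.7 | 2.0 |
| 8 | 5.3% | 5.3 points | 1.8 | 5.3 |
| 15 | 10.0% | 10.0 points | 3.4 | 10.0 |

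The gap is a bound between two definitions, not an estimate of bias. With N = 120, k = 2, 6 and 12 give 1.7, 5.0 and 10.0 points.

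**Step 4: effect on a reported rate (exact 95% intervals).** Start from 99/150 = 66.0% (57.8 to 73.5). Counting treated responders as failures gives:

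- k = 3: 96/150 = 64.0% (55.8 to 71.7)
- k = 8: 91/150 = 60.7% (52.4 to 68.5)
- k = 15: 84/150 = 56.0% (47.7 to 64.1)

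From 120/150 = 80.0%, the rate seen at 6 months in earlier work (10.5), k = 15 gives 105/150 = 70.0% (62.0 to 77.2).

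**Step 5: what the per-protocol repeat does.** If all 15 treated responders are known and dropped from the 99/150 case, the result is (99 − 15)/(150 − 15) = 84/135 = 62.2% (53.5 to 70.4). Counting them as failures gives 56.0%. The repeat answers a different question, and only for treatments on record.

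**The case against.** The plan is not without safeguards. Protocol 14.3 requires every deviation on an eCRF, and section 9 includes checks of protocol compliance and CRF review to study exit. SAP 3.6 removes deviations that may affect interpretation of the primary and major secondary endpoints from the per-protocol set. SAP 2.2.1 also removes events that might affect NOSE scores, so a known valve treatment could be excluded even under the 12-month reading. All of this stands for treatments the site knows about. None of it makes the site ask.

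Three stronger readings are tempting, and the documents do not support them.

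- **That dilator use is certainly missed.** The update in 7.1.4 is still required on its face. The blank cell in 7.7 is weak evidence of the contrary, because the same row is blank at Early Exit although 7.8 requires medication changes there. Dilator capture is uncertain; the gap for procedures is clearer.
- **That about 10% will be retreated.** In the first study 3 of 30 (10%; exact interval 2.1% to 26.5%) had other nasal surgery after month 12 (Protocol 2.2). The type is not stated, and septoplasty and turbinate reduction are not on the 7.6 list. One of the three came after the 18-month visit. Those subjects left that study and had had no septal or turbinate treatment in it (2.3.3), unlike many who may enrol here. It is not a reliable rate.
- **That a late conclusion would be overturned.** From 99/150, 11 treated responders leave 88/150 = 58.7% (50.3 to 66.6; p = 0.041) and 12 leave 87/150 = 58.0% (49.7 to 66.0; p = 0.060). From 120/150 it would take 33. In any case 50% decides nothing at these visits: Protocol 10.2 states no other formal hypothesis, SAP 4.1.1 makes other p-values descriptive, and Protocol 10.4.9 calls these endpoints supportive.

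**Conclusion.** The point holds as a gap in ascertainment and one conflicting time limit, and it should be corrected. Following the plan as written, a subject retreated after month 12 can be counted as an 18- or 24-month responder without anyone knowing. If the treatment is known, the only provision is to drop the subject from a supporting analysis.

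The reach is limited. The 6-month primary and the 12-month results are not affected. Under assumed treatment rates of 2% to 10%, the late responder rate differs between the two definitions by at most 2 to 10 points. True inflation is smaller unless none of the treated subjects would have responded anyway. The real frequency is unknown. The contents of the 18- and 24-month forms and the exit form are not in the documents, so a question may exist there. Confidence is therefore moderate.

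**What to change.** **Protocol.** Apply 24 months to the nasal-valve bullet in 7.6. Mark concomitant medications at Visits 8 and 9 in 7.7, to agree with 7.1.4. At both contacts, ask about any nasal procedure for obstruction since the last visit, naming septoplasty and turbinate reduction, and about dilator use, with dates. Septoplasty and turbinate reduction need naming because 7.6 does not list them.

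**SAP.** Keep the observed 18- and 24-month responder rates as the main result. Add one sensitivity analysis that counts as non-responders those with a nasal procedure for obstruction, or another 7.6 treatment, before that assessment. Repeat the VAS model without values recorded after such treatment.

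**Cost.** One bullet, one table row, a few questions at two contacts that already take place, and two short additional analyses. The sensitivity rate is conservative: it may fail some subjects who would have responded anyway, for example after occasional use of a nasal strip. That is why it should not replace the observed rate. The questions matter most, since treatment not asked about at these contacts may be hard to recover later.

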7.7. STUDY SCHEDULE OF EVENTS TABLE

Study Events	Screening & Enrollment (Visit 1)	Baseline Evaluation (Visit 2) ¹	Treatment (Visit 3)	Follow Up 1 mo (Visit 4)	Follow Up 3 mo (Visit 5)	Follow Up 6 mo (Visit 6)	Follow Up 12 moStudy Visit (Visit 7)	Follow Up 18 & 24 mo/Final Study Visit (Visits 8 & 9)	Early Exit
Secure Informed Consent	Х								
Secure Re-Consent for 18M and 24M Follow Up							Х		
Inclusion/Exclusion	Х		X ²						
NOSE Scale (PRO) ³	Х	Х	X ²	Х	Х	Х	Х	Х	
NAO Breathing Assessment (PRO)		Х		Х	Х	Х	Х	Х	
Subject Satisfaction Questionnaire (PRO)				Х	Х	Х	Х		
Health Economics Questionnaire (PRO)		Х		Х	Х	Х	Х		
Nasal Medical History/Nasal Geometry		Х							
Nasal Exam		Х		Х	Х	Х	Х		
Lateral Wall Motion Video		Х				Х			
Photography- 3D Camera (select sites)		Х			Х	Х	Х		
Photography –Cosmetic (select sites)		Х			Х	Х			
Turbinate Hypertrophy Contribution to		Х							
NAO assessment (Nasal Decongestant)									
Photography – Planning Images			Х						
NAO Treatment			Х						
Concomitant Medications		Х	Х	Х	Х	Х	Х		
Adverse Event Assessment			X	X	X	X	Х		Х
Adverse Device Effects Assessment								X	
Complete Study Exit Form								X ⁴	Х

¹ Visit 2 activities may be done in conjunction with Study Visit 1. In this instance, the Screening NOSE Scale is not required.

² If Visit 3 (Treatment Visit) is more than 1 month after Visit 1, inclusion/exclusion criteria need to be re-confirmed. Additionally, subjects should be asked to review IC form, initial and date the IC document to confirm continued consent for participation, and complete NOSE scale.

³ If Visits 1, 2 and 3 are done on the same day, the Screening and Treatment NOSE Scales are not required.

⁴To be completed at 24M follow up.

Spirox Latera™ implant support of lateral wall cartilage (LATERAL-OR) study	
SPI-CP-301	Sep

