5. STUDY ENROLLMENT AND WITHDRAWAL

5.1. PARTICIPANT INCLUSION CRITERIA

In order to be eligible to participate in this study, an individual must meet all of the following inclusion criteria:

- 1. The subject has NOSE Score \geq 55.
- 2. The subject has dynamic lateral nasal wall insufficiency as confirmed by positive Modified Cottle Maneuver.
- 3. The subject is ≥ 18 years of age.
- 4. The subject is willing and able to provide informed consent and comply with the study protocol.
- 5. The subject is seeking treatment for nasal airway obstruction due to Nasal Valve Collapse (NVC) and is willing to undergo nasal Implant procedure alone or with septoplasty and/or a turbinate reduction procedure in an operating room setting.
- 6. The subject has appropriate nasal and facial anatomy to receive Latera Implant.
- 7. The subject agrees to follow-up examinations through twelve (12) months post operatively.
- 8. The subject has failed to benefit from appropriate maximal medical management [e.g., nasal steroids (at least 4 weeks); antihistamines; oral decongestants; nasal strips, stents, or cones]. Failure of maximal medical management may be from lack of effectiveness or inability of subject to tolerate.

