7. STUDY PROCEDURES AND SCHEDULE

7.1. STUDY VISIT SPECIFIC PROCEDURES

7.1.1. Subject Screening and Enrollment Visit (Visit 1)

All subjects seeking treatment for nasal obstruction will be screened for eligibility, according to inclusion/exclusion. A member of the research team will review the subject's medical history for eligibility and inclusion into the study.

Female subjects that may be pregnant will undergo a pregnancy test per the individual study sites' standard operating procedures.

The subject will be asked to fill out a NOSE score questionnaire and a NOSE score will be calculated. If all inclusion criteria (including NOSE score \geq 55) are met and no exclusion criteria are present, the Investigator will inform the subject about the purpose of the study. The background of the proposed study along with the potential benefits and risks will be explained to the subject and questions will be answered. Potential subjects will be counseled as to the nature of their condition. All subjects will have ample time to ask questions.

Subjects who indicate they would like to proceed with study participation, and who are willing to comply with the requirements of the study protocol, will be asked to sign an Informed Consent Form (ICF) that has been approved by the governing IRB. Failure to provide written informed consent renders the subject ineligible for the study.

Subjects that have signed the ICF and meet the eligibility criteria will be scheduled for Visit 2. Subjects will be considered enrolled upon signing the ICF and meeting the study eligibility criteria.

Study data should be entered into the EDC within 24 hours of completion of visit.

Subjects that have provided written informed consent and meet the eligibility criteria may also be invited to participate in "Latera™ Patient Experience and Testimonials" (see Section 7.2.15).

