7.2. STUDY EVALUATIONS METHODS

7.2.1. Nasal Obstruction Symptom Evaluation (NOSE) Scale

The Nasal Obstruction Symptom Evaluation (NOSE) Scale¹⁸ is a Patient-Reported Outcome (PRO) instrument that will be administered to capture subject perception of the degree of nasal airway patency. The NOSE scale will be completed at the Screening, Baseline, 1 Month, 3 Month, 6 Month, 12 Month, 18 Month and 24 Month visits. The NOSE scale may additionally be completed at the Treatment Visit if more than 1 month from Screening Visit.

The NOSE scale is a validated instrument, which was developed by the American Academy of Otolaryngology—Head and Neck Surgery (AAO-HNS), and has been used in several clinical trials. The scale is brief, easy to complete, and is an important tool for pre- and post-intervention evaluation of symptoms in subjects with nasal obstruction. NOSE Scale allows subjects to quantify their symptoms based on the severity of obstruction.

Subjects will be asked, "Since your last follow up visit, how much of a problem were the following conditions for you?" Specifically, subjects will be asked to rate their perceptions on the Likert scale with respect to the following characteristics:

- Nasal congestion or stuffiness
- Nasal blockage or obstruction
- Trouble breathing through my nose
- Trouble sleeping
- Unable to get enough air through my nose during exercise or exertion

Participants will rate their responses using a Likert scale with response options 0, 1, 2, 3 or 4, as follows:

- (0) Not a Problem
- (1) Very Mild Problem
- (2) Moderate problem
- (3) Fairly Bad Problem
- (4) Severe problem

The responses are rated along the continuum, with a rating of "0 – not a problem" indicating no problem breathing, with a completely free flow of air through the nasal airway; "1 – very mild problem", with only slight obstruction in airflow; "2 – moderate problem", with mouth breathing considered easier; "3 – fairly

Spirox Latera™ implant support of lateral wall cartilage (LATERAL-OR) study	Version 2.0
SPI-CP-301	September 7, 2017

bad problem," with considerable obstruction to airflow; and a rating of "4 – severe problem," with complete blockage and obstruction of the nasal passageway, where the subject cannot breathe through the nose and can only mouth breathe. A copy of the Nasal Obstruction Symptom Evaluation Scale questionnaire is attached (See Addendum B).

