10.4. DESCRIPTION OF STATISTICAL METHODS

10.4.1. GENERAL APPROACH

This is a prospective, single arm, open label controlled study to evaluate the impact of Spirox Latera[™] alone or in conjunction with other procedures over 24 months of follow-up. Each patient will serve as his or her own control.

The study reference day (Day 1) is the day of the Implant procedure.

"Baseline" NOSE score refers to the measurement taken prior to the start of the procedure during the baseline visit.

Continuous variables will be summarized with descriptive statistics (N, mean, SD, median, quartiles), and categorical variables will be summarized as N (%).

Unless otherwise indicated, all p-values and confidence intervals will be 2-sided.

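### When Visits 1 and 2 are combined and treatment follows within a month, the NOSE score that qualifies a subject is also the baseline for response, so some regression to the mean is counted as response and no planned analysis shows how much

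*Protocol*

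**What the plan says.** Protocol 5.1, first inclusion criterion, sets the threshold: "The subject has NOSE Score" of 55 or more. Protocol 7.1.1 has the score obtained at Visit 1: "The subject will be asked to fill out a NOSE score questionnaire and a NOSE score will be calculated".

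Two footnotes to the schedule in Protocol 7.7 then reduce the number of scores. When Visits 1 and 2 share a day: "Visit 2 activities may be done in conjunction with Study Visit 1. In this instance, the Screening NOSE Scale is not required". When all three visits share a day: "If Visits 1, 2 and 3 are done on the same day, the Screening and Treatment NOSE Scales are not required". Protocol 7.2.1 adds a treatment-day score only after a delay: "The NOSE scale may additionally be completed at the Treatment Visit if more than 1 month from Screening Visit".

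The baseline is defined in three ways:
- Protocol 10.4.1: the "measurement taken prior to the start of the procedure during the baseline visit".
- SAP 2.1: the pre-implant measure nearest to Day 1.
- SAP 4.2.1: the within-subject average of the pre-implant scores.

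A responder improves by at least one NOSE class or by at least 20%. The study has a single arm, each subject is the control for himself or herself (Protocol 4.1), and the test is against a fixed 0.50 (Protocol 10.2, SAP 1.3). The supportive analyses in SAP 4.2.2.1 address protocol deviations and missing data only.

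**The concern.** A score that had to be high for the subject to enter is, on average, partly high by chance, so the next score tends to fall with no treatment effect. If that same score is the baseline, the fall is counted as improvement. A concurrent control arm would show the same fall and remove it. Here it passes into the responder proportion and its confidence interval.

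The response rule adds to this. The entry cut-off of 55 is also the lower edge of the severe class, so a subject who enters at exactly 55 becomes a responder with one 5-point step to 50.

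Averaging does not help a subject who has one score. For a subject with two, the average in SAP 4.2.1 still contains the qualifying score. Neither document mentions regression to the mean or says that 0.50 allows for it.

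**Working it through.** **1. How many scores exist.**

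| Path | Pre-implant NOSE scores | Is the qualifying score the baseline? |
|---|---|---|
| Visits 1 and 2 separate | screening and baseline | No under Protocol 10.4.1; partly under the SAP 4.2.1 average |
| Visits 1 and 2 combined, treated within 1 month | one | Yes, under all three definitions |
| All three visits on one day | one | Yes, under all three definitions |
| Treated more than 1 month after Visit 1 | one more, at Visit 3 | Depends on which definition governs |

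**2. The plan's own figure.** Both documents state power above 90% at a true rate of 66% against 0.50, with a two-sided exact test at 5%. This is reproduced. With 150 evaluable subjects (Protocol 10.5) the smallest successful count is 88 (88/150 = 58.7%) and power is 97.5%. With 120 (SAP 1.4) it is 72 (60.0%) and power is 93.0%.

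**3. Smallest fall that counts as response.** It is 5 points from 55 or 80; 10 from 60 or 85; 15 from 65, 70, 75 or 90; and 20 from 95 or 100.

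**4. Anchor for the enrolled mean.** The prior study in Protocol 2.2 used the same threshold. Its week-1 mean was 24.2 after a mean change of -52.5, so its baseline mean was 24.2 + 52.5 = 76.7.

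**5. Simulation.** Each setting has 1,000,000 subjects. Observed score = true score + independent error, rounded to 5 and limited to 0 to 100. Subjects are kept if the qualifying score is at least 55, and the plan's response rule is applied. The following are assumptions, not in the documents: SD 18 before selection, test-retest reliability 0.6 to 0.9, and unselected mean 60, 70 or 75. Means 70 and 75 give enrolled means of 75.0 and 78.0, which bracket 76.7. Mean 60 gives 69.9.

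Three effects were tried: no change, a uniform 10-point fall, and a mean fall of 43 with between-subject SD 28. The last is set from the prior study's 6-month change of -43.3 (SD 31.28): at reliability 0.7, 28² + 2 × 18² × 0.3 = 978.4, and √978.4 = 31.28.

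Responder rate against the qualifying score versus a separate pre-implant score:

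| Unselected mean, reliability | No change | 10-point fall | Fall of 43, SD 28 |
|---|---|---|---|
| 60, 0.6 | 36.4% vs 27.9% | 62.2% vs 52.0% | 88.3% vs 85.5% |
| 70, 0.6 | 29.3% vs 25.4% | 54.3% vs 49.1% | 86.1% vs 84.6% |
| 70, 0.9 | 14.6% vs 12.6% | 50.8% vs 47.7% | 86.9% vs 86.5% |
| 75, 0.9 | 12.9% vs 11.5% | 46.7% vs 44.6% | 86.1% vs 85.8% |

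For means 70 to 75 the excess is about 1.4 to 4 points with no change, 2 to 5 with a 10-point fall, and 0.3 to 1.6 with the prior-study effect. At mean 60 it reaches 8 to 10 points in the first two cases and 2.8 in the third.

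A wider grid (mean 55 to 75, SD 15 to 20) gives an excess of 0.9 to 11.8 points with no change. The highest no-change responder rate in that grid is 42.0%.

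**6. What averaging leaves.** In that grid, at mean 70, SD 20, reliability 0.6 and no change, the rates are 31.2% (qualifying score), 28.0% (average of two) and 26.4% (separate score). The average keeps 28.0 - 26.4 = 1.6 of the 31.2 - 26.4 = 4.8 points.

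**7. Effect on the test at 150 subjects.** The chance of reaching 88 responders is about 82% at a rate of 62% and about 6% at 52%. At 42%, the highest no-change rate, it is about 0.

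**The case against.** The strongest reply is that the effect is small where it matters. The only baseline evidence in the documents points to an enrolled mean near 76.7, where the excess is a few points. The prior trial showed 80% response at 6 months and planning used 66%, where power is 97.5%. Separate visits are the scheduled default and combining them is optional, so only some subjects carry the excess. The combined visits are a deliberate convenience in a post-market study that says openly that it is neither randomized nor blinded. All of this stands, and it limits the size of the point.

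It does not remove the point. Even when the verdict is safe, the reported proportion and interval are shifted upward by an amount that no planned analysis shows.

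A reader might go further and infer that regression to the mean could make this trial positive by itself, or that it is likely to decide the result. The documents do not support either. With no true change, no setting exceeded 42.0%, against the 58.7% needed. The contrast of 62.2% with 52.0% needs a weak uniform effect, an enrolled mean of 69.9 and a single score in every subject. Placebo response, natural course and the concurrent septoplasty or turbinate surgery are separate matters and were not modelled.

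A fair objection also applies to the remedy. After 1 month the Visit 3 NOSE form is completed alongside re-confirmation of eligibility (Protocol 7.1.3 and the 7.7 footnotes), so that score may itself be a qualifying score.

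**Conclusion.** The point holds in a limited form. For single-score subjects the qualifying score is the baseline under every definition in the two documents, and part of any later fall is selection.

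The size rests on assumed reliability, SD and unselected mean. With an enrolled mean near 76.7, single-score subjects gain about 1.4 to 4 points with no true change, 2 to 5 with a uniform 10-point fall, and under 2 with an effect like the prior study's. The trial-level excess is lower, because the share of single-score subjects is unknown and below one if any visits are separate. For example, if half had one score and the others a clean baseline, 4 points would become 0.5 × 4 = 2. The verdict of the test could change only if the true effect is weak. It is a matter for correction by a cheap addition, not a reason to doubt the design as a whole.

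**What to change.** 1. Have every subject who is treated on a later day than the qualifying score complete the NOSE form before the procedure at Visit 3. The form is already used there after 1 month. This is data collection only and need not alter eligibility.
2. Reconcile the baseline definitions in Protocol 10.4.1, SAP 2.1 and SAP 4.2.1. Otherwise the new score would be ignored, used alone or averaged, depending on which text governs.
3. Add to SAP 4.2.2.1 a repeat of the primary analysis whose baseline is a pre-implant score not used to establish or re-confirm eligibility: the separate Visit 2 score, or the Visit 3 score where it was not part of re-confirmation.
4. Report the number and responder rate of subjects who have only a qualifying score.

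The cost is one 5-item form and one supportive analysis. Some reference scores will lie below 55, and subjects with all three visits on one day cannot contribute to item 3. If enrollment is complete, items 2 to 4 can still be done with the scores collected.
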